Study Objectives	
 • The coprimary objectives of this study are to: 
 ○ Assess the logistics and feasibility of subcutaneous delivery of abatacept early post-transplant and the accrual and retention of study subjects during the first year after transplant to inform the potential design and conduct of further clinical development including Phase II and/or Phase III trials. ○ Explore the effectiveness (freedom from rejection) and safety (such as adverse events, serious adverse events, infections, cardiovascular, metabolic side-effects) of a regimen substituting subcutaneous abatacept for belatacept as a means of facilitating the improvement of long-term graft function by reducing exposure to calcineurin inhibitor-based immunosuppression. • Secondary objectives also include: 
 ○ Additional assessments of effectiveness 
 ▪ Renal allograft graft function: measurement of the levels, stability and trajectory of renal function (eGFR) in abatacept treated patients to inform the design of future prospective, randomized studies ▪ Renal allograft survival ▪ De novo donor-specific antibody formation ○ Mechanistic and biomarker studies with a focus on pharmacokinetics, pharmacodynamics (target receptor occupancy), T and B cell subsets (eg. Tregs).
Study Design	
Phase I, open-label, prospective, single-arm single center study evaluating the feasibility, effectiveness and safety of a regimen substituting subcutaneous abatacept early post-transplant in place of intravenous belatacept as an immunosuppressant in first-time renal transplant recipients.
 
There is a single arm in this study; Investigational (abatacept) group. Participants will be assigned to treatment regimen between 2 and 5 months after transplantation. The study drug will be administered until month 12

	post-transplant; at that point, all participants will be transitioned to a physician directed immunosuppressive regimen post-study. Study endpoints will be assessed at 12 months after transplantation.
Primary Endpoint(s)	
Primary feasibility endpoint The proportion of subjects who tolerate subcutaneous injections and are compliant with self-administration as measured by abatacept administration logs and autoinjector accountability.
 
Primary Effectiveness (alloimmunity) endpoint This primary effectiveness endpoint is the proportion of participants who remain free of biopsy proven acute T-cell mediated rejection (aTCMR) or antibody-mediated rejection (ABMR) as defined by Banff criteria at or before 12 months after transplantation.
 
Primary Safety Endpoints
 
 • The cumulative incidence of serious adverse events • Incidence of serious infection of special interest (e.g. requiring hospitalization or prolonged therapy, including but not limited to treatment ≥ 20 days) • Incidence of patients with CMV viremia stratified by magnitude (≥ 35 but $< 10,000$ or $\geq 10,000$) • Incidence of patients with BK viremia stratified by magnitude (undetected, > 0 but $< 1,000$, $\geq 1,000$ but $< 10,000$ or $\geq 10,000 - 100,000$, $\geq 100,000$ or stratified by log, which is reported as a result.) • Incidence of any malignancy including PTLN
Secondary Endpoint(s)	
Additional Effectiveness Endpoints
 
 • Proportion of subjects experiencing the composite outcome of death or allograft failure at or before 12 months after transplantation. • Proportion of subjects with biopsy proven acute T-cell mediated cellular rejection (BP-aTCMR) within 12 months of transplantation. • Proportion of subjects treated for rejection with any of the following: i) corticosteroids within 12 months, ii) T-cell depleting therapy within 12 months, iii) any other treatment for rejection within 12 months of transplantation • Proportion of subjects treated for acute rejection due to clinical suspicion rather than BP-aTCMR or BP-aABMR within 12 months of transplantation. • Proportion of subjects with biopsy proven active antibody mediated rejection (BP-aABMR) within 12 months of transplantation. • Proportion of subjects and time to event for the changes in allograft biopsies for the 5 categories of aTCMR specified in the Banff schema. • Proportion of subjects who develop de-novo donor specific antibody by 12 months. • Change in eGFR between abatacept initiation and 12 months on treatment. • Days to events (TCMR, ABMR, de-novo DSA formation, graft loss).
Exploratory Endpoints	
Clinical Patient preferences and attitudes toward subcutaneous and intravenous

	
route of administration will be assessed based on questionnaires administered at enrollment and at study visits at month 6 and 12 post initiation of abatacept.
 
Immunologic/Mechanistic
 
 • CD86 receptor occupancy on PBMC will be assessed before the initial dose of abatacept, and prior to abatacept administration at months 9, and 12 months post-transplantation. • The incidence and breadth of anti-HLA antibody (including DSA) development over time (evaluated at screening, , 3, 6 and 12 post-transplant) • Peripheral blood T and B cell subsets will be assessed before initiation of abatacept and on study at 6, 9, and 12 months post - transplant.
Accrual Objective	18 patients will be enrolled into a single, investigational arm receiving abatacept
Study Duration	20 months, with the last new accrual no later than 12/31/2023.
Treatment Description	
Participants on qualifying belatacept regimen (with low dose tacrolimus, mmf and prednisone) will have their maintenance regimen changed from i.v. belatacept to s.c. abatacept, which will continue through week 52 (month 12) post-transplant:
 
Costimulation blockade:
 
 - Abatacept 125 mg subcutaneous weekly 
Background maintenance:
 
 - Tacrolimus initial trough target 3-5 ng/ml. - Mycophenylate mofetil (MMF), no less than 500 mg bid; comparable dose of mycophenolic acid (MPA) (no less than 360 mg bid) or azathioprine (AZA no less than 2mg/kg daily) may be used instead as maintenance dose. - Prednisone 5 mg po daily.
Inclusion Criteria	
 1. Must be able to understand and provide informed consent. 2. Male or Female, 18-70 years of age at the time of enrollment (all races and ethnicities). 3. Negative crossmatch (virtual or physical) at time of transplant 4. First dose of Study Drug must be given no less than 8 weeks, no more than 20 weeks post-transplant. 5. First time renal transplant who has been treated with belatacept from the time of transplant, receiving tacrolimus (target trough 3-5 ng/ml), mycophenylate mofetil (or mycophenolic acid or azathioprine), prednisone (also see exclusion criteria). 6. eGFR ≥ 40ml/min/m² (using 2021 CKD-EPI equation). 7. Must have prior documented evidence of EBV seropositivity.

	
 8. Female study participants of childbearing potential must have a negative pregnancy test on Day 0 prior to receiving the first dose of study drug . 9. Agreement to use contraception; according to the FDA Office of Women's Health (http://www.fda.gov/birthcontrol), there are a number of birth control methods that are more than 80% effective. Female study participants of child-bearing potential and men must consult with their physician and determine the most suitable method(s) from this list to be used from the time that study treatment begins until after study completion- 10. Vaccines up to date as per DAIT guidance for patients in transplant trials. (Refer to Appendix 2: DAIT Vaccine Guidance for Patients in Interventional Adult Transplant Trials) 11. Study participants must have a negative purified protein derivative (PPD) or negative testing for tuberculosis using an approved IGRA blood test, such as QuantiFERON®-Gold TB or T-SPOT-TB assay. PPD or IGRA testing must be documented to have been performed within the 52 weeks before enrollment. Patients with latent TB may become eligible according to local or national guidelines following completion of treatment.
Exclusion Criteria	
 1. Inability or unwillingness of a study participant to give written informed consent or comply with study protocol. 2. Recipient of previous organ transplant of any type. 3. Multi-organ transplant. 4. cPRA >80 at time of enrollment. 5. History of any episode of biopsy-proven Banff rejection (including borderline rejection or any grade of acute TCMR) prior to enrollment. 6. History of any malignancy including lymphoma within 5 years of enrollment. Study participants with curatively treated non-melanomatous skin cancer or curatively treated cervical carcinoma in situ may be enrolled. 7. Any past or current issue which in the opinion of the investigator may pose additional risks to the participant in the study, may interfere with the study participant's ability to comply with the study requirements or that may impact the quality or interpretation of the data obtained from the study. 8. Human immunodeficiency virus (HIV): individuals known to be HIV positive. 9. Hepatitis C virus: any study participant who receives a kidney from a seropositive or HCV RNA PCR positive donor is ineligible. Any study participant who was HCV RNA PCR positive at transplant is ineligible. Any study participant with a history of HCV seropositivity or HCV infection who has not met criteria for sustained spontaneous clearance or sustained viral response to therapy is ineligible. 10. Hepatitis B virus: Individuals with any of the following are NOT eligible: 
 • Recipient or donor positive for hepatitis B surface antigen (HBsAg) • Recipient or donor positive for antibodies to hepatitis B core antigen (anti-HBc) • Recipient or donor known to have had a positive HBV DNA

	
PCR
 
 11. Evidence of CMV viremia or clinical CMV infection at any time after transplant. 12. Kidney recipients who were CMV seronegative who received an organ from a CMV seropositive donor. 13. BK viremia of greater than 4.3 DNA log copies/ml (greater than 20,000 copies/ml) at any time post-transplant. 14. Active uncontrolled infection within 1 month of enrollment. 15. Clinically significant proteinuria (urinary protein/Cr ratio >1.0). 16. Receiving belatacept at a dose other than 5 mg/kg body weight. 17. Receiving mycophenolate mofetil at a dose of less than 1000 mg po QD (or mycophenolic acid or azathioprine equivalent). 18. Receiving prednisone at a dose greater than 5 mg po qd. 19. Presence of donor specific antibody by Luminex single antigen bead assay.
Study Stopping Rules	
Satisfaction of any of the following stopping rules at any time during the post-transplant follow-up will trigger an ad hoc DSMB Safety Review.
 
 • Any unexpected fatal, or unanticipated life-threatening adverse event that is possibly or definitely related to the study treatment regimen or procedures • 2 Deaths • 2 Graft losses • 2 Incidences of BP-aTCMR Banff IIB or Banff III • 2 malignancies or life-threatening infections • 4 rejections in total (biopsy-proven or empirically treated) 
In addition to the mandated stopping rule thresholds noted, NIAID DSMB, NIAID medical/scientific observer, may pause enrollment after any single death, graft loss, Banff II, Banff III, malignancy or life-threatening infection event.

Participant Stopping Rules	
Participants may be prematurely terminated from the study intervention for the following reasons.
 
 1. The participant elects to withdraw consent from all future study activities, including follow-up. 2. The investigator or NIAID medical officer no longer believes that participation or treatment in the trial is in the best interest of the participant. 3. Study therapy may be prematurely discontinued for any participant if the participant has severe injection related hypersensitivity or injection related reaction. 4. Occurrence of Banff grade IIb or higher grade acute rejection 5. The participant dies. 
For subjects that terminate the study intervention, limited follow-up for safety events and clinical outcomes will continue unless the subject withdraws consent for any further follow-up.

Acute Rejection	A clinical and histologic event that meets the Banff 2017 revised criteria for acute cellular rejection.
Antibody Mediated Rejection	A clinical and histologic event that meets the Banff 2017 revised criteria for antibody mediated rejection.
Banff 2017 Scoring Criteria (Kidney)	
Reference & further details given in Roufosse C, et al. A 2018 Reference Guide to the Banff Classification of Renal Allograft Pathology. Transplantation 2018; 102: 1795-1814.
 
https://banfffoundation.org/wp-content/uploads/2019/01/A_2018_Reference_Guide_to_the_Banff_Classification.14-1.pdf
 
Category 1: Normal biopsy or nonspecific changes
 
Category 2: Antibody-mediated rejection Active ABMR Chronic, active ABMR C4d Staining without Evidence of Rejection
 
Category 3: Borderline changes Suspicious (Borderline) for acute TCMR
 
Category 4: T-cell-mediated rejection (TCMR) Acute TCMR (Grade IA, IB, IIA, IIB, III) Chronic Active TCMR (Grade I1, IB, II)

Donor Specific Antibodies	The presence of antibodies against antigens encoded by the HLA (human leukocyte antigen) complex that are expressed on the donor allograft.
Empirically treated rejection	Initiation of any treatment for rejection (e.g. steroids 10mg/kg or Thymoglobulin).
Graft Failure/Loss	
Graft loss occurs when a graft is deemed irreversibly nonfunctional and is the earliest of the day that:
 
 • dialysis which continues for six consecutive weeks is begun, or • a transplant nephrectomy is performed, or • The participant is re-listed for kidney transplantation, or • Has an eGFR <15 for a period of 8 weeks.
Modified Intent-to-Treat Sample	All enrolled participants who receive at least a single dose of the study intervention (abatacept)
Investigational Agent	Abatacept ORENCIA®
Lost to Follow-up	Missing in-person follow-up visits and cannot be reached by telephone or mail.
NIAID Medical/Scientific Observer	NIAID staff who regularly meets with the protocol director/principle investigator and study team including sponsor-appointed medical monitor, to review the progress of the study, safety events, and reporting.
NIAID Project Manager	NIAID staff who coordinates key study activities, including maintaining versions of protocols and amendments, informed consent templates, study management calls with investigators, coordinators, and other study personnel.
Per Protocol Sample	Completes all study visits and has not had a protocol deviation that impacts the analysis

Principal Investigator	Investigator awarded NIH funding for the grant.
Program Officer	NIAID official who oversees the scientific and budgetary aspects of the grant.
Protocol Mandated Procedures	Any procedure performed solely for the purpose of this research study, not considered site-specific standard of care.
Regulatory Affairs Officer	IND sponsor staff responsible for regulatory aspects of the study, for studies when NIAID is not the IND sponsor.
Principal Investigator	Investigator awarded NIH funding for the grant.
Study Therapy Regimen	The investigational agent and all protocol required medications.
Women of Child-Bearing Potential	WOCBP includes any female who has experienced menarche and who has not undergone successful surgical sterilization (hysterectomy, bilateral tubal ligation, or bilateral oophorectomy) or is not postmenopausal (defined as amenorrhea \geq 12 consecutive months), or women on hormone replacement therapy with documented serum follicle stimulating hormone levels >35 mIU/mL). Even women who are using oral, implanted, or injectable contraceptive hormones or mechanical products such as an intrauterine device or barrier methods (diaphragm, condoms, spermicide) to prevent pregnancy or practicing abstinence or where the partner is sterile (e.g., vasectomy), should be considered to be of child-bearing potential.

1. Study Hypotheses/Objectives

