7.1.4. Modification of immunosuppression protocol

If a participant cannot tolerate at least 2 consecutive doses of abatacept or 3 total doses or the site investigator determines that modification of the assigned immunosuppression regimen is in the best interest of the participant, the site investigator will modify the immunosuppression regimen for that participant. This will result in the participant being censored from the Per Protocol analysis of the assigned arm at that point. This would not be considered a protocol deviation.

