12.2.1. Follow-up for Participants Prematurely Discontinued from Study Therapy

Study subjects who discontinue study therapy will continue to be followed with all scheduled study assessments and sample collection, unless the subject withdraws consent from all future study activities, including follow-up.

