12.3 Participant Stopping Rules and Withdrawal Criteria

Participants may be prematurely terminated from the study intervention for the following reasons.

1. The participant elects to withdraw consent from all future study activities, including follow-up.
2. The investigator or NIAID medical officer no longer believes that participation or treatment in the trial is in the best interest of the participant.
3. Study therapy may be prematurely discontinued for any participant if the participant has severe injection related hypersensitivity or injection related reaction.
4. Occurrence of Banff grade IIb or higher grade acute rejection
5. The participant dies.

For subjects that terminate the study intervention, limited follow-up for safety events and clinical outcomes will continue unless the subject withdraws consent for any further follow-up.

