14.2 Endpoints/Analysis Plan

All analyses will be detailed in the statistical analysis plan. All analyses will be performed using the SAS System version 9.4 (or higher).

14.2.1 Analysis Populations.

Modified Intent-to-treat (mITT) sample – all enrolled subjects who start abatacept therapy. Subjects who receive drug but who do not remain on the protocol regimen will be used in this population. Enrolled subjects who do not receive any doses of abatacept will be excluded from this population.

Per Protocol (PP) sample – all enrolled subjects who receive abatacept and who remain on the assigned maintenance immunosuppressive regimen without major protocol deviations of concern.

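### Three conflicting per-protocol rules, no analysis set named for any endpoint, and contradictory follow-up after study drug stops: the PP estimate can shift either way, and month-12 eGFR and DSA may go missing

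*Combined protocol and SAP*

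**What the plan says.** **Per-protocol sample.** Three places define it or act on it.

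- Glossary: a participant who "Completes all study visits and has not had a protocol deviation that impacts the analysis". Staying on the regimen is not mentioned.
- Section 14.2.1: "all enrolled subjects who receive abatacept and who remain on the assigned maintenance immunosuppressive regimen without major protocol deviations of concern". Attending visits is not mentioned.
- Section 7.1.4, for a participant who cannot tolerate abatacept or whose regimen the investigator changes: "This will result in the participant being censored from the Per Protocol analysis of the assigned arm at that point". It adds: "This would not be considered a protocol deviation".

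**mITT sample.** The glossary and section 14.2.1 agree: everyone who receives abatacept, including those who later leave the regimen.

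**Which sample for which endpoint.** Sections 14.2.2 to 14.4 do not say.

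**Ending the intervention.** Section 12.3 and the synopsis list reasons for which it may be ended. They include death and "Occurrence of Banff grade IIb or higher grade acute rejection". Section 12.2 lists intolerance as a reason to discontinue study therapy.

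**Follow-up afterwards.** Section 12.3 and the synopsis: "limited follow-up for safety events and clinical outcomes will continue unless the subject withdraws consent for any further follow-up". Section 12.2.1: "Study subjects who discontinue study therapy will continue to be followed with all scheduled study assessments and sample collection", unless consent is withdrawn. Section 6.5 keeps those who discontinue in the study so that endpoints can be assessed.

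**The concern.** Completing every visit and remaining on the regimen are both known only after baseline, and both can depend on how the participant fared. A PP sample built on them selects on outcome. Censoring at the regimen change is a different analysis again: the participant counts up to the change, and any later rejection is lost. With 18 participants, moving one or two people between samples shifts the effectiveness estimate by several percentage points. The trial is open-label and no primary sample is named, so the choice could be made after the results are known.

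The follow-up conflict affects the data themselves. Staff who apply the limited rule could omit month-12 creatinine and DSA samples in participants who stopped abatacept because of rejection or intolerance. The eGFR levels and variability from this trial are meant to inform later trials, so such a gap would carry forward.

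**Working it through.** **Plan's own figure.** The plan gives no number on this point. Its one quantitative design statement, the section 13.9 table for n = 18, reproduces in all 12 cells (for example 1 − 0.90^18 = 0.850) and is not in dispute.

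**Step 1: apply the three PP rules to the same participant.**

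| Participant who has started abatacept | Glossary | 14.2.1 | 7.1.4 |
|---|---|---|---|
| Dies before month 12 | Out: visits incomplete | Not addressed | Not addressed |
| Stops for intolerance, attends every visit | Can be in | Out | In until the change |
| Regimen changed after Banff IIb or higher rejection, attends every visit | Can be in, event counted | Out, event goes too | Event before the change counted |
| First rejection after a regimen change, attends every visit | Can be in, event counted | Out | Event not counted |
| Lower-grade rejection, stays on regimen, attends every visit | In | In | In |
| Misses one visit, on regimen, no event | Out | In | In |

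Only the fifth row gets the same clear answer from all three.

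**Step 2: size for freedom from rejection.** Inputs: n = 18 (synopsis: "18 patients will be enrolled into a single, investigational arm receiving abatacept"). The documents give no expected rejection rate, so 3 rejections are assumed. Intervals are 95% Wilson with continuity correction, the section 14.4 method.

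| Who is excluded | Rejection-free | Estimate (95% CI) |
|---|---|---|
| Nobody (mITT) | 15/18 | 83.3% (57.7 to 95.6) |
| One non-rejector, e.g. a death without rejection | 14/17 | 82.4% (55.8 to 95.3) |
| Two non-rejectors, e.g. intolerance | 13/16 | 81.3% (53.7 to 95.0) |
| One rejector | 15/17 | 88.2% (62.3 to 97.9) |
| Two rejectors | 15/16 | 93.8% (67.7 to 99.7) |
| Three rejectors | 15/15 | 100% (74.7 to 100) |

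Under 7.1.4 censoring, suppose one of the three rejections follows a regimen change and nobody else is censored. Kaplan-Meier then sees two events. If the censoring precedes both, the estimate is 15/17 = 88.2%. If it falls between them, it is 17/18 × 15/16 = 88.5%. If it follows both, it is 16/18 = 88.9%. All exceed 83.3%.

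**Step 3: size if limited follow-up removes month-12 values.** If k of 18 are unobserved and their mean eGFR lies D below the rest, the raw observed mean is too high by k × D / 18. With assumed k of 1 to 3 and D of 10 to 30 units, the shift runs from 1 × 10/18 = 0.6 to 3 × 30/18 = 5.0 units. For example, two participants at 30 and sixteen averaging 55 give (16 × 55 + 2 × 30)/18 = 52.2 against an observed 55.0.

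For DSA, if the only two de novo cases (assumed) are among those not sampled, 2/18 = 11.1% (1.9 to 36.1) becomes 0/16 = 0% (0 to 24.1).

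Under the section 12.2.1 rule with mITT, these shifts vanish apart from deaths and withdrawn consent.

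**The case against.** A reader might infer that PP drops everyone who rejects and so drives freedom from rejection to 100% by construction. The documents do not support that.

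- Only Banff IIb or higher is listed in section 12.3, and as a reason for which the intervention may be ended. Sections 7.1.1 and 7.1.3 allow mycophenolate or azathioprine and prednisone to be adjusted, so a treated lower-grade rejection need not take anyone off the regimen.
- Section 7.1.4 keeps a rejection that came before the change.
- Death is not part of the rejection endpoint. Removing a participant who died without rejection, or stopped without rejection, removes a success and lowers the PP estimate.

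A reader might also infer that the eGFR and DSA results lose the failures. That is conditional. It needs the limited rule to be applied and its undefined clinical outcomes to leave out eGFR and DSA. Sections 12.2.1 and 6.5 point the other way. Section 12.5 lists creatinine and HLA antibody at a final visit after withdrawal, though participants may, rather than must, be asked to attend. Earlier eGFR values stay in the mixed model, so the raw-mean shifts above are not the model's bias. If stopping follows a recorded fall in eGFR, missing at random may hold approximately.

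Finally, mITT is defined and keeps these participants, no endpoint is assigned to PP, and a supportive on-regimen sample is ordinary in a descriptive phase I study.

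All of this stands and limits the claim. It does not reconcile the three PP rules, commit the plan to mITT, or say which follow-up text governs.

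**Conclusion.** The point holds as an unresolved conflict that permits bias, not as a demonstrated bias toward success. The PP rules are incompatible, and each can remove participants or events for reasons that arise after baseline. The direction depends on who leaves: with 3 assumed rejections in 18, from 81.3% to 100% against 83.3% in mITT. This range rests on assumed counts.

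The follow-up sections contradict each other on data collection. If the limited rule is applied and leaves out eGFR and DSA, their month-12 values will be missing for those who stopped. The eGFR model is then valid only under missing at random, and the plan gives no rule or sensitivity analysis for missing DSA. Section 14.2 defers detail to a statistical analysis plan. If one outside the reviewed text names the sample for each endpoint, that part of the point falls away.

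**What to change.** 1. In section 14.2.1, name mITT as the primary sample for the effectiveness, safety, eGFR and DSA endpoints, with PP supportive.
2. Use one PP definition in the glossary, 7.1.4 and 14.2.1, based on eligibility and abatacept exposure up to the first rejection, graft loss or death. Exclude nobody because of an outcome, its treatment or a visit missed after it. State how participants switched off abatacept before any event are handled. Amend the sentence in 7.1.4 on deviation status to match; otherwise someone switched early for intolerance could count as a full-year PP success.
3. Reconcile the synopsis and section 12.3 with 12.2.1 and 6.5 on data collection: scheduled creatinine/eGFR, DSA and rejection assessments continue to month 12 after study drug stops, unless consent is withdrawn. This concerns data only. How participants are treated after stopping is not at issue.

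Cost: amended wording in the protocol and analysis plan. Some participants off drug will have more visits than under the limited rule, and the PP result may look less favourable.
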